- AEs, actions taken as a result of AEs, and follow-up results must be recorded in the patient's medical record.
- In addition, patients will receive a follow up phone call 6-months post FMT and every subsequent 6 months for the next year to record any SAEs, new medical conditions and diagnoses, or changes in conditions or diagnoses since last study contact.

For all SAEs and AEs, relevant clinical assessments and laboratory tests will be repeated as clinically appropriate, until final resolution or stabilization of the event(s).

All AEs including local and systemic reactions not meeting the criteria for SAEs will be captured on the appropriate electronic case report form (eCRF). Information to be collected includes event description, time of onset, clinician's assessment of severity, relationship to study product (assessed only by those with the training and authority to make a diagnosis), and time of resolution/stabilization of the event. All AEs occurring while on study must be documented appropriately regardless of relationship. All AEs will be followed to adequate resolution.

Any medical condition that is present at the time that the participant is screened will be considered as baseline and not reported as an AE. However, if the study participant's condition deteriorates at any time during the study, it will be recorded as an AE.

Changes in the severity of an AE will be documented to allow an assessment of the duration of the event at each level of severity to be performed. AEs characterized as intermittent require documentation of onset and duration of each episode.

Study coordinators will record all reportable events with start dates occurring any time after informed consent is obtained until 7 (for non-serious AEs) or 30 days (for SAEs) after the last day of study participation. At each study visit, the investigator will inquire about the occurrence of AE/SAEs since the last visit. Events will be followed for outcome information until resolution or stabilization.

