4.2 Inclusion Criteria

1. Male or Female \geq 18 years of age.
2. Documentation of prior history of mild to moderate UC.
3. Endoscopy confirmed active UC \geq 15 centimeters at day 0 screening colonoscopy.

- a. As defined by a total Mayo scoring of 4-10 with an endoscopic sub-score ≥ 1 and a stool frequency or rectal bleeding sub-score of ≥ 1 .
4. Patients must have a descending intact colon.
5. Patients taking steroid or biologic therapy must be on a stable dose for 4 weeks prior to screening and maintained throughout the trial.
6. Eligible patients willing to undergo serological and fecal screening testing prior to FMT to document baseline status:
 - a. Urine Testing
 - i. Pregnancy test (women with childbearing potential)
 - b. Blood Testing
 - i. B-HCG (research purposes)
 - ii. CBC, ESR, CRP, and BMP (standard of care)
 - iii. HIV, type I and II (standard of care)
 - iv. Hepatitis A B C Profile (standard of care)
 - v. RPR (*treponema pallidum*) (research purposes)
 - vi. CMV IgM (standard of care)
 - vii. Quantiferon-TB (standard of care)
 - c. Stool Testing
 - i. Calprotectin (standard of care)
 - ii. Clostridium Difficile Toxin PCR (standard of care)
 - iii. Ova & parasites (standard of care)
 - iv. Gastrointestinal Pathogen PCR Panel (standard of care)
 1. *Campylobacter* species
 2. *Plesiomonas Shigelloides*
 3. *Salmonella* Species
 4. *Vibrio* Species
 5. *Vibrio cholerae*
 6. *Yersinia Enterocolitica*
 7. Enterotoaggregative *E. coli* (EAEC)
 8. Enteropathogenic *E. coli* (EPEC)
 9. Enterotoxigenic *E. coli* (LT/ST)
 10. Shigalike toxin producing *E.coli* I (STX/ST2)
 11. *Cryptosporidium*
 12. *Cyclospora cayetanensis*
 13. *Entamoeba cayetanensis*
 14. *Giardia*
 15. *Adenovirus* F 40/41
 16. *Astrovirus*
 17. *Norovirus* GI/GII
 18. *Rotavirus* A
 19. *Sapovirus*
 20. *GID* PCR INTERP

7. Patients must discontinue anti-rCDI antibiotics (e.g. vancomycin, fidaxomicin) 48 hours prior to FMT delivery procedure.

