13.3 AE/SAE Follow Up

All SAEs and AEs reported during this study require the investigator to follow them until resolution or until the investigator confirms that the AE/SAE has stabilized and no more follow-up is required. This requirement indicates that follow-up may be required for some events after the subject discontinues participation from the study. Resolution is defined as:

- a. Resolved with or without residual effects
- b. Return to baseline for a pre-existing condition
- c. Fatal outcome; if autopsy is performed, the autopsy report must be provided to the sponsor.

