13.4 Time Period and Frequency for Event Assessment**13.4.1. AE/SAE Monitoring**

Each enrolled subject will be monitored for the occurrence of AEs, including SAEs, beginning immediately after FMT. The occurrence of an adverse event (AE) or serious adverse event (SAE) may come to the attention of study personnel during study visits and interviews of a study participant presenting for medical care, or upon review by a study monitor. Subjects will be questioned at each follow up time-point about unsolicited and solicited AE on stool form and frequency, presence of abdominal pain, fevers and subjective well-being and/or examined (at day

1, 2, 6, 10 and 12 weeks post-FMT via phone call; 4 and 8 weeks post-FMT via office visit and review of patient diary for AE monitoring) by the treating physician for evidence of AEs. The questioning of subjects with regard to unsolicited adverse events will be generalized such as, "How have you been feeling since your last visit?". The following AEs will be solicited via phone calls and clinic visits by a study coordinator, along with the intensity of each:

1. Fever
 - a. Mild: Temperature 37.7-38.6°C
 - b. Moderate: Temperature 38.7-39.3°C
 - c. Severe: Temperature 39.4-40.5°C
 - d. Potentially Life Threatening: Temperature >40.5°C
2. Chills
 - a. Mild: No or minimal interference with usual social and functional activities
 - b. Moderate: Greater than minimal interference with usual social and functional activities
 - c. Severe: Inability to perform usual social and functional activities
3. Fatigue/Malaise
 - a. Mild: No or minimal interference with usual social and functional activities
 - b. Moderate: Greater than minimal interference with usual social and functional activities
 - c. Severe: Inability to perform usual social and functional activities
 - d. Potentially Life Threatening: Incapacitating fatigue or malaise symptoms causing inability to perform basic self-care functions.
4. Anorexia (loss of appetite)
 - a. Mild: Loss of appetite without decreased oral intake
 - b. Moderate: Loss of appetite with decreased oral intake without significant weight loss
 - c. Severe: Loss of appetite with decreased oral intake associated with significant weight loss
 - d. Potentially Life Threatening: Life threatening consequences or aggressive intervention indicated (TPN or tube feeding)
5. Abdominal Pain
 - a. Mild: Pain causing no or minimal interference with usual social and functional activities.

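### The solicited adverse-event scale is not given before treatment, so for most items the baseline-and-deterioration rule rests on ungraded judgment

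*Combined protocol and SAP*

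**What the plan says.** Section 13.4.1 sets two rules on symptoms that predate treatment. A condition "present at the time that the participant is screened will be considered as baseline and not reported as an AE". The second rule is the exception to the first: a worsening of such a condition on study does become an AE. Section 13.3 counts as resolution, among other outcomes, "Return to baseline for a pre-existing condition". All three need a pre-treatment level.

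The graded questions come only later. Section 13.4.1 opens with "Each enrolled subject will be monitored for the occurrence of AEs, including SAEs, beginning immediately after FMT", and then: "The following AEs will be solicited via phone calls and clinic visits by a study coordinator, along with the intensity of each". The nine items are fever, chills, fatigue/malaise, anorexia, abdominal pain, constipation, diarrhea, nausea and vomiting. They are tied to the follow-up time points. The screening list (6.1.1) and the day 0 list (6.1.2.1) do not include them, and the adverse-event row of Table 1 appears to begin at day 0.

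Everyone enters with active disease, "As defined by a total Mayo scoring of 4-10 with an endoscopic sub-score" of at least 1 and a stool frequency or rectal bleeding sub-score of at least 1 (4.2). Psyllium starts on day -3 (6.1.1, 7.1.2).

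**The concern.** Pain, fatigue, poor appetite and loose stools can be expected in many people with active colitis. When a coordinator records moderate abdominal pain at week 2, the plan gives no entry grade to compare it with. Two errors become possible. Long-standing symptoms may be recorded as AEs, which adds the same kind of background to every arm and shrinks the differences between arms. Or a real worsening may be put down to baseline and not recorded.

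The percentage of patients with at least one AE (15.3) inherits this uncertainty. So may the review trigger in 15.4, which fires when more than 10% of subjects have the same Grade 3 event, if the solicited intensities are what defines Grade 3. The documents do not say whether they are.

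**Working it through.** **1. What is graded before treatment, item by item**

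| Solicited item | Reference to entry status in 13.4.1 | Graded pre-treatment record |
|---|---|---|
| Abdominal pain, fatigue, nausea | None | No item grade; the Mayo physician's global assessment takes in abdominal discomfort and well-being as one composite, 0-3 |
| Anorexia | Severe depends on weight loss | No appetite grade; weight is measured at screening |
| Diarrhea, mild and moderate | One limb counts stools over baseline; the other (unformed or watery stools) does not | Mayo stool frequency, 0-3 |
| Diarrhea, severe | One limb is an increase of 7 or more stools; bloody diarrhea qualifies alone | Mayo rectal bleeding, 0-3, but the item does not refer to it |
| Fever, chills, constipation, vomiting | None | No item grade; vital signs at screening |

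The full Mayo score is taken on day 0 (10.1.1.1). Its stool item is relative to the patient's normal and stops at 5 or more extra stools. It cannot give the 24-hour count from which increases of up to 3, 4-6 and 7 or more are measured. It is also taken after psyllium has started. The diary named in 13.4.1 is for post-FMT monitoring and has no row in Table 1.

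**2. Plan figures**

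The documents state no power for safety. Their only power figure, about 80% for 55% against 27% response with 45 per arm (12.1), computes to 78.0% by the normal approximation and is not affected here.

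**3. Size of the dilution (illustration)**

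Contrast: FMT with or without fiber (90) against placebo FMT (45), which is one of the safety comparisons in 12.1.

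Assumptions, none of them document figures: true rate of new or worsened events h = 20% on FMT and 5% on placebo; entry prevalence b; a share m of persisting entry symptoms recorded as AEs; independence. With r the share of entry symptoms that resolve,

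observed rate = 1 - (1 - m·b·(1 - r))·(1 - h).

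With no resolution (r = 0) the observed difference is (1 - m·b) × 15 points. For example, with b = 0.5 and m = 1: 1 - 0.5 × 0.80 = 60.0% against 1 - 0.5 × 0.95 = 52.5%, a difference of 7.5 points.

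| b | m = 1: difference, power | m = 0.5: difference, power |
|---|---|---|
| 0 | 15.0, 66% | 15.0, 66% |
| 0.3 | 10.5, 21% | 12.75, 34% |
| 0.5 | 7.5, 13% | 11.25, 24% |
| 0.7 | 4.5, 9% | 9.75, 19% |

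Power is two-sided at 0.05, by the normal approximation.

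**4. When the sign would change**

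Now let entry symptoms resolve at the plan's response rates, 27% (FMT alone) and 7% (diet alone). With m = 1 the difference is +6.0, 0.0 and -6.0 points at b = 0.3, 0.5 and 0.7. It is zero where 0.80(1 - 0.73mb) = 0.95(1 - 0.93mb), that is mb = 0.15/(0.8835 - 0.584) = 0.50. With 41% resolution on FMT, the mean of 27% and 55%, the threshold is 0.15/(0.8835 - 0.472) = 0.36. With m = 0.5 and r = 27% against 7%, the differences stay positive: +10.5, +7.5 and +4.5 points.

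**5. The 15.4 trigger**

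Take 135 as the denominator and Severe as Grade 3, both assumptions. More than 13.5 subjects means 14. The binomial chance of 14 or more of 135 is 0.8%, 19.2%, 48.5%, 95.4% and 99.9% if the share scored Severe on one item is 5%, 8%, 10%, 15% and 20%. Entry bleeding scored as bloody diarrhea in 15% of subjects would then very probably start a review without any treatment harm.

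**The case against.** The plan is not without a baseline. Screening has a medical history, physical examination, weight, CRP, ESR, CBC and calprotectin. The day 0 Mayo grades stool frequency, bleeding and a global assessment that covers abdominal discomfort. A clinician assesses severity, changes in severity must be documented, and causality assessment must weigh the disease under treatment and pre-existing conditions (13.4.2.2). Diarrhea is partly graded against baseline. Recurrent flare is kept out of AE reporting (13.2.4). Several listed safety measures, such as treatment-related events, hospitalizations, surgeries and mortality (12.4.2), need not be inflated by ordinary entry symptoms. All of this stands, and so the rule is usable in an ungraded way.

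It does not supply an entry grade for pain, fatigue, appetite or nausea, or a stool count. Randomization balances entry symptoms in expectation, but it does not undo dilution.

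A reader might go further and infer that the rule cannot be applied at all, or that colitis symptoms will swamp or reverse a harm signal. The documents do not support either reading. Reversal needs high entry prevalence, nearly all persisting symptoms counted as AEs despite the baseline rule, and more symptom resolution on active treatment. It also treats Mayo response as full symptom resolution, which a reduction of more than 3 points and more than 30% is not.

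**Conclusion.** The gap is real and narrow. Section 13.4.1 defines AEs for pre-existing conditions, and 13.3 defines their resolution, by reference to a level that the plan does not record for most of the solicited items. Staff must rely on ungraded judgment that can differ between raters. The expected effect is dilution of the solicited-AE contrasts. In the no-resolution case it is a factor of 1 - m·b, where b is the entry prevalence and m the share of persisting symptoms counted as AEs. The documents give neither, so the figures above show a range and are not a forecast. Reversal of sign is a conditional extreme case. The effect on the 15.4 trigger depends on which scale defines Grade 3, and that is not stated. Efficacy sample size and power do not change. It is worth acting on because the correction is cheap and the missing entry grades cannot be reliably recovered later.

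**What to change.** - Give the nine-item solicited checklist, with the 13.4.1 intensities, and a 24-hour stool count at screening before psyllium starts on day -3. Repeat both on day 0 before infusion, asking about the days before bowel preparation. Add them to 6.1.1, 6.1.2.1 and Table 1.
- Keep deterioration as the AE definition in 13.4.1, and state that it is judged against the recorded entry level in grade, frequency or duration. Requiring a higher grade would narrow the present rule, because more frequent or longer symptoms within a grade would be lost.
- As an added table, report by arm the solicited events that are new or above the entry grade, up to week 8 and before the second FMP250 dose. Use the screening value as reference for psyllium contrasts.
- Reconcile the start of AE capture. Section 13.4.1 says that subjects "will be monitored for the occurrence of AEs, including SAEs, beginning immediately after FMT", and 12.6.1 counts toxicity from the first FMP250 treatment, but 13.4.1 also records events with "start dates occurring any time after informed consent is obtained". The choice decides whether days -3 to 0 on psyllium are covered.
- State which severity scale defines Grade 3 in 15.4: CTCAE version 5.0 (13.1.11), the item scales in 13.4.1, or the general definitions in 13.4.2.1.

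Cost: one CRF page and a few minutes at two existing visits, with no added procedure, staff or patients. The downside is slightly longer screening and day 0 visits.

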13.4.2. AE/SAE Assessment

13.4.2.1 Assessment of Severity

The severity of AEs will be assessed according to the following definitions:

- Mild: The AE is noticeable to the patient and/or the Investigator but does not interfere with routine activity.
- Moderate: The AE interferes with routine activity but responds to symptomatic therapy or rest.
- Severe: The AE significantly limits the patient's ability to perform routine activities despite symptomatic therapy.
- Life-threatening/disabling: The AE puts patient at risk of death. This does not refer to an event that may hypothetically have caused death if it were more severe.

13.4.2.2 Assessment of Causality

The physician must assess the relationship of any AE (including SAEs) to FMT, as related or not related, based on clinical judgment and using all available information, and may include consideration of the following factors:

- a. Possible alternative causes of the AE, including the disease under treatment, pre-existing conditions, concomitant use of other drugs, and presence of environmental or genetic factors.
- b. The temporal association between FMT exposure and onset of the AE.
- c. Whether the manifestations of the AE are consistent with known actions or theoretical toxicity of FMT.

The causal relationship between FMT and the AE will be assessed using one of the following categories:

- a. Not Related: An AE is not associated with FMT if:
 - An event that can be determined with certainty to have no relationship to the FMT.
 - Temporal relationship is lacking (i.e. the event did not occur within a reasonable time frame following administration of FMT)

[figure not shown]
- Other causative factors more likely explain the event (i.e. pre-existing condition, other concomitant treatments);
- b. Definitely Related:
 - There is a positive temporal relationship (i.e. the event occurred within a reasonable time frame following FMT)
 - The AE is more likely explained by FMT than by another cause
 - Previously known toxicity of FMT.
- c. Probably Related:
 - There is a positive temporal relationship (i.e. the event occurred within a reasonable time frame following FMT)
 - The AE is more likely explained by FMT than by another cause
 - Unlikely to be explained by patient's clinical state or other intervention.
- d. Possibly Related:
 - There is a positive temporal relationship (i.e. the event occurred within a reasonable time frame following FMT)
 - Event follows an expected response pattern to FMT, but event could have occurred secondary to a number of other factors.

14. Unanticipated Problems Involving Risks to Subjects or Others

14.1 Definition of Unanticipated Problems Involving Risks to Subjects or Others (UPIRTSO)

The Office for Human Research Protections (OHRP) considers unanticipated problems involving risks to participants or others to include, in general, any incident, experience, or outcome that meets all of the following criteria:

- Unexpected in terms of nature, severity, or frequency given (a) the research procedures that are described in the protocol-related documents, such as the Institutional Review Board (IRB)-approved research protocol and informed consent document; and (b) the characteristics of the participant population being studied;
- Related or possibly related to participation in the research ("possibly related" means there is a reasonable possibility that the incident, experience, or outcome may have been caused by the procedures involved in the research); and
- Suggests that the research places participants or others at a greater risk of harm (including physical, psychological, economic, or social harm) than was previously known or recognized.

14.1.2 Unanticipated Problem Reporting

The sub-investigators will report unanticipated problems (UPIRTSOs) to the reviewing Institutional Review Board (IRB) and to the lead principal investigator (PI). The UPIRTSO report will include the following information:

- Protocol identifying information: protocol title and number, PI's name, and the IRB project number;
- A detailed description of the event, incident, experience, or outcome;
- An explanation of the basis for determining that the event, incident, experience, or outcome represents an UPIRTSO;
- A description of any changes to the protocol or other corrective actions that have been taken or are proposed in response to the UPIRTSO.

To satisfy the requirement for prompt reporting, UPIRTSOs will be reported using the following timeline:

- UPIRTSOs that are serious adverse events (SAEs) will be reported to the IRB within 1 week of the investigator becoming aware of the event.
- Any other UPIRTSO will be reported to the IRB within 2 weeks of the investigator becoming aware of the problem.
- All UPs should be reported to appropriate institutional officials (as required by an institution's written reporting procedures), the supporting agency head (or designee), Food and Drug Administration (FDA), and the Office for Human Research Protections (OHRP) within one month of the IRB's receipt of the report of the problem from the investigator.

15. Data and Safety Monitoring Plan (DSMP)

A Weill Cornell Medicine Data Safety Monitoring Board (WCM DSMB) will monitor the data collected in this clinical trial on a quarterly basis to ensure the safety of enrolled subjects. The first periodic report to the DSMB will be within 3 months after enrolling the first subject and will be submitted through the

following link: <https://research.weill.cornell.edu/integrity-compliance/research-support/human-research/data-safety-monitoringboard/make-submission>. This monitoring plan was chosen for this clinical trial because it will be randomized and is intended to provide definitive information on the effectiveness and safety of FMTs and fiber supplements in active UC patients.

We will minimize the risk of UC relapse/flare by maintaining close clinical contact with all enrolled subjects. They will be encouraged to contact the clinical team if they experience recurrence of diarrhea, fever or abdominal pain so that further work up can be initiated, and escalation of standard therapy as appropriate. Solicited and unsolicited AEs will be recorded at day 1, week 2, week 6, week 10, week 12, 6 months, and every subsequent 6 months for 1-year post-FMT via phone calls and at 4 weeks, 8 weeks, and 12 weeks via clinic visit by any study team member. They will record any SAEs, new medical conditions/diagnoses or changes in medical conditions/medications since last study contact. If any events are noted during these follow-up evaluations, they will promptly be reported and reviewed by the treating physician and/or lead PI.

15.1. Plan for informed consent compliance

Written, informed consent will be obtained from each subject prior to the performance of any study procedures or assessments. Prior to enrolling a subject into the study, a designated member of the study team will explain the study protocol as outlined in the informed consent, procedures and objectives to the subject and/or authorized representative. When the subject, or legally authorized representative agrees to participation in the clinical trial, he/she or authorized representative must understand, sign and date the IRB approved Informed Consent Document which describes the study and potential discomforts, risks and benefits of participating. One copy of the consent form will be provided to the subject and one copy will be maintained with the subject's permanent medical records.

